4.2.1. Study Population

Participants enrolled in this study will have inadequately controlled T2DM (as indicated by HbA1c at screening) on diet and exercise alone. Participants will be allowed to take certain concomitant medications as outlined in [Section 6.5](#).

Both females of childbearing potential, as well as those who are of non-childbearing potential, will be enrolled given the availability of EFD toxicity studies with PF-06882961. However, as marketed GLP-1R agonists are listed as contraindicated in pregnancy, measures will be taken to limit the risk of pregnancy in the female population enrolled (see [SOA](#) and [Appendix 4](#)).

4.2.2. Pharmacokinetic Parameters

This study will include plasma sampling to examine the Day 1 and steady-state PK of PF-06882961.

CCI

CCI

[figure not shown]
4.3. Justification for Dose

4.3.1. Selection of Dose Levels

In this study, PF-06882961 will be administered BID at three dose-levels for 8 weeks. Identical starting dose and weekly titration steps in this study are being utilized in the non-Japanese phase 2 study (C3421005). The dose-titration scheme and the target dose level are shown in [Table 3](#). The PF-06882961 doses selected for this study and the non-Japanese phase 2 study (C3421005) are based on observed safety, tolerability, PK, [CCI](#) from the non-Japanese phase 1 study (C3421002); as well as the exposure margins relative to completed nonclinical toxicology studies. Exposure margins for the highest proposed dose in this study (120 mg BID) are given in [Section 2.2.1.3](#).

For the high-dose arm, 120 mg BID, the maximum dose in the non-Japanese phase 2 study (C3421005), has been selected to evaluate the safety and tolerability of PF-06882961 in Japanese participants with T2DM so that safety and tolerability can be examined in the dose range including the maximum potential dose in the planned global phase 3 studies.

With regard to the results from the non-Japanese phase 1 study (C3421002), target doses ranging from 10 mg BID to 120 mg BID were generally safe and well tolerated, as described in [Section 2.2.2.1](#). Forty mg BID and 80 mg BID, which are the middle doses in the non-Japanese phase 2 study (C3421005), have been selected as the low-dose and the middle-dose arms, respectively. [CCI](#)

4.4. End of Study Definition

A participant is considered to have completed the study if he/she has completed all phases of the study including the follow up visit (V12), approximately 28 to 35 days post last dose of study intervention.

The end of the study is defined as the date of the last visit (V12) of the last participant in the study.

5. STUDY POPULATION

This study can fulfill its objectives only if appropriate participants are enrolled. The following eligibility criteria are designed to select participants for whom participation in the study is considered appropriate. All relevant medical and nonmedical conditions should be taken into consideration when deciding whether a particular participant is suitable for this protocol.

Prospective approval of protocol deviations to recruitment and enrollment criteria, also known as protocol waivers or exemptions, is not permitted.

5.1. Inclusion Criteria

Participants are eligible to be included in the study only if all of the following criteria apply:

Age and Sex:

1. Male and female participants must be 20 to 70 years of age, inclusive, at the time of signing the ICD.
 - Refer to [Appendix 4](#) for reproductive criteria for male ([Section 10.4.1](#)) and female ([Section 10.4.2](#)) participants.

Type of Participant and Disease Characteristics:

2. Participants with T2DM who are treated with diet and exercise, and are taking no antidiabetic medications.
3. HbA1c $\geq 7\%$ and $\leq 10.5\%$ at screening (Visit 1) as assessed by the study specific laboratory and confirmed by a single repeat test, if deemed necessary.
4. Participants who are willing and able to comply with all scheduled visits, treatment plan, laboratory tests, lifestyle considerations, and other study procedures, including the ability to perform self-tests of blood sugar regularly (see [Section 8.2.5.1](#)) for the duration of the study and maintenance of study specific glucose logs for the duration of participation in the study.

Body Mass Index (BMI) and Weight:

5. Total body weight >50 kg (110 lb) with BMI of 22.5 to 45.4 kg/m². Body weight must have been stable (<5% change) for 90 days prior to screening (Visit 1) as per participant report.

Informed Consent:

6. Capable of giving signed informed consent as described in [Appendix 1](#), which includes compliance with the requirements and restrictions listed in the ICD and in this protocol.

5.2. Exclusion Criteria

Participants are excluded from the study if any of the following criteria apply:

Medical Conditions:

1. Evidence or history of clinically significant hematological, renal, endocrine, pulmonary, gastrointestinal, cardiovascular, hepatic, psychiatric, neurological, or allergic disease

(including drug allergies, but excluding untreated, asymptomatic, seasonal allergies at the time of dosing).

- Participants who have chronic conditions other than T2DM (for example, hypercholesterolemia or hypertension) but are controlled by either diet or stable doses of medications may be included. See [Section 6.5](#) for further information on concomitant medications.

2. Any condition possibly affecting drug absorption (eg, prior bariatric surgery, gastrectomy, or any area of intestinal resection, active inflammatory bowel disease or pancreatic insufficiency).
3. Diagnosis of type 1 diabetes mellitus or secondary forms of diabetes, or a history of ketoacidosis.
4. History of myocardial infarction, unstable angina, arterial revascularization, stroke, New York Heart Association Functional Class II - IV heart failure, or transient ischemic attack within 6 months of screening (Visit 1).
5. Any malignancy not considered cured (except basal cell carcinoma and squamous cell carcinoma of the skin); a participant is considered cured if there has been no evidence of cancer recurrence in the previous 5 years.
6. Personal or family history of MTC or MEN2, or participants with suspected MTC per the investigator's judgment.
7. History of acute or chronic pancreatitis.
8. Symptomatic gallbladder disease.
9. Participants with a known medical history of active proliferative retinopathy and/or macular edema.
10. History of HIV infection, hepatitis B, or hepatitis C; positive testing for HIV, HepBsAg, HepBcAb, HCVAb or syphilis. Hepatitis B vaccination is allowed.
11. Known intolerance or hypersensitivity to GLP-1R agonists.
12. Other medical or psychiatric condition including recent (within the past year) or active suicidal ideation/behavior or laboratory abnormality that may increase the risk of study participation or, in the investigator's judgment, make the participant inappropriate for the study.

Prior/Concomitant Therapy:

13. See [Appendix 8](#) for details regarding prohibited prior/concomitant medications.

Prior/Concurrent Clinical Study Experience:

14. Previous administration with an investigational drug within 4 months or 5 half-lives preceding the first dose of study intervention used in this study (whichever is longer).
15. Known prior participation in a trial involving PF-06882961.

Diagnostic Assessments:

16. Screening supine BP ≥ 160 mmHg (systolic) or ≥ 100 mmHg (diastolic), following at least 5 minutes of supine rest. BP should be measured in triplicate and the average of the 3 BP values should be used to determine the participant's eligibility.
17. Screening 12-lead ECG that demonstrates clinically relevant abnormalities that may affect participant safety or interpretation of study results (eg, QTcF interval >450 msec, complete LBBB, signs of an acute or indeterminate-age myocardial infarction, ST-T interval changes suggestive of myocardial ischemia, second- or third-degree AV block, or serious bradyarrhythmias or tachyarrhythmias).
 - If QTcF exceeds 450 msec, or QRS exceeds 120 msec, the ECG should be repeated 2 more times and the average of the 3 QTcF or QRS values should be used to determine the participant's eligibility.
18. A positive urine drug test. **Note:** Participants who have been medically prescribed opiates/opioids or benzodiazepines and report the use of these drugs to the investigator at screening (Visit 1) may be allowed to participate with notification to the sponsor.
19. Participants with **ANY** of the following abnormalities in clinical laboratory tests at screening, as assessed by the study-specific laboratory and confirmed by a single repeat test, if deemed necessary:
 - AST **or** ALT level $\geq 2 \times$ ULN;
 - TBili level $\geq 1.5 \times$ ULN; participants with a history of Gilbert's syndrome may have direct bilirubin measured and would be eligible for this study provided the direct bilirubin level is \leq ULN.
 - Fasting C-peptide <0.8 ng/mL.
 - TSH $>1.5 \times$ ULN.
 - Serum calcitonin $>$ ULN.
 - Amylase or lipase $>$ ULN.
 - Fasting blood glucose >270 mg/dL (15.0 mmol/L).

- eGFR <60 mL/min/1.73 m² as calculated by the CKD-EPI equation. ¹⁴

20. FSBG on Day -2 of >270 mg/dL (15.0 mmol/L).

Other Exclusions:

21. History of regular alcohol consumption exceeding 7 drinks/week for female participants or 14 drinks/week for male participants (1 drink = 5 ounces [150 mL] of wine or 12 ounces [360 mL] of beer or 1.5 ounces [45 mL] of hard liquor) within 6 months prior to screening.
22. Known or suspected illicit drug use.
23. Blood donation (excluding plasma donations) of approximately 400 mL for the past 3 months or 200 mL for the past 1 month prior to dosing and participants who are planning for blood donation for 3 month after the last dose of study intervention.
24. History of sensitivity to heparin or heparin-induced thrombocytopenia only if heparin is planned to flush intravenous catheters.
25. Unwilling or unable to comply with the criteria in the Lifestyle Considerations section of this protocol.
26. Investigator site staff or Pfizer employees directly involved in the conduct of the study, site staff otherwise supervised by the investigator, and their respective family members.

5.3. Lifestyle Considerations

The following guidelines are provided:

5.3.1. Meals and Dietary Restrictions

- Participants must abstain from all food and drink (except water) at least 8 hours prior to CCI [REDACTED] the collection of the first blood sample (eg, glucometer measurement, safety laboratory, PK CCI [REDACTED] assessment) at Screening, each inpatient study day, each outpatient visit, and the follow-up visit.
- Water may be consumed as desired (ad libitum).
- Noncaffeinated drinks (except grapefruit or grapefruit-related citrus fruit juices - see below) may be consumed with meals and the evening snack.
- Participants will not be allowed to eat or drink grapefruit or grapefruit-related citrus fruits (eg, Seville oranges, pomelos) from 7 days prior to the first dose of study intervention until collection of the final PK blood sample.

- Details on the meals provided to participants at Visit 2 through Visit 10, including the menu items, portion sizes and approximate calories with nutritional macronutrient (% carbohydrate, fat and protein) breakdown of the meal will be maintained in source documentation at the site. This information will not be collected in the CRF, however may be submitted to the Sponsor upon request.
- On scheduled visits to the site, ***in the morning***, from Visit 2 through Visit 10, participants should be instructed to arrive **without** having morning meal/breakfast or self-administration of study intervention. ***Note:*** Participants may take their morning dose of antihypertensive and/or lipid modifying medication per their usual routine, if applicable.
- At Visit 2 through Visit 10, inclusive, the morning meal will be consumed with the study intervention at the site.
- Participants will be counseled on appropriate dietary and exercise guidelines for T2DM at Visit 2 and asked to maintain these guidelines throughout participation in the study. Counseling on dietary guidelines should be in accordance with local medical standards of care for patients with T2DM. ***Note:*** Participation in formal weight loss programs is prohibited during participation in this study.

5.3.1.1. Admission days (Days -2 and 55)

- The caloric intake/menu assigned to each participant will be based on the Harris Benedict formula (sedentary lifestyle; to be provided to the site prior to study start) using the participant's body weight measured at screening.
- Participants will not be required to consume all provided food during standard meals.
- A standard breakfast will be provided with dosing at approximately 0800 hours on Day 55 and at approximately the same time on Day -2.
- Lunch will be provided approximately 4 hours after AM dosing (approximately 1200 hours) Day 55 and at approximately the same time on Day -2.
- Dinner will be provided with dosing approximately 10 hours after AM dosing (approximately 1800 hours) Day 55 and at approximately the same time on Day -2.
- An evening snack may be provided at approximately 2200 hours.
 - Participants will receive the same snack each evening prior to the MMTT the following day. Participants will be encouraged to consume the entire evening snack.

5.3.1.2. During inpatient days (Days -1, 1, 56 and 57)

- The caloric intake/menu assigned to each participant will be based on the Harris Benedict formula (sedentary lifestyle; to be provided to the site prior to study start) using the participant's body weight measured at screening.
- On days with MMTT as listed in [Table 2](#) of the [SOA](#) (including evening snack prior to MMTT) **only**: participants will be encouraged to consume all provided food, including the liquid meal and all standard meals provided on these days. In addition, the approximate percentage of food consumed should be recorded in CRF.
- Participants will not be required to consume all provided food during standard meals on Day 1 and Day 57.
- When a meal or snack is scheduled at the same time as an ECG, the meal will be provided after the ECG is completed.
- Breakfast will be provided with dosing at approximately 0800 hours each day while inpatient:
 - A standard breakfast will be provided on Day 1 with dosing and Day 57 except when the MMTT is administered;
 - For the MMTT, the mixed meal will be provided as 500 mL of ENSURE® H and will be administered as listed in [Table 2](#) of the [SOA](#). The entire ENSURE® H meal is to be consumed within approximately 10 minutes. (See [Section 8.6.1](#)).
- Lunch will be provided approximately 4 hours after AM dosing (approximately 1200 hours). On days with MMTT, lunch will be provided after the 4-hour postdose blood collection samples for the MMTT have been completed.
- Dinner will be provided approximately 10 hours after AM dosing (approximately 1800 hours).
- An evening snack may be provided at approximately 2200 hours.
- Meals on days with MMTT, will be standardized such that the participants receive the same menus for all meals on these days:
 - Participants will be encouraged to consume their entire meals on Days -1 and 56;
 - If participants do not consume their entire meal on Day -1, they will be instructed to consume the same amount of food ($\pm 10\%$) on the other days with MMTT that they ate on Day -1. If a participant consumes approximately $<90\%$ or $>110\%$ of what s/he consumed on Day -1 based on visual inspection by the site staff, the approximate percentage consumed should be noted on the source document;

- The start time of all meals will be captured in the CRF on days with MMTT including the ENSURE® H mixed-meal provided for breakfast.
- Participants will be encouraged to eat all standard meals within 30 minutes on days with MMTT administration;

5.3.1.3. Discharge days (Days 2 and 58)

- The caloric intake/menu assigned to each participant will be based on the Harris Benedict formula (sedentary lifestyle; to be provided to the site prior to study start) using the participant's body weight measured at screening.
- Participants will not be required to consume all provided food during standard meals.
- A standard breakfast will be provided with dosing at approximately 0800 hours each day.

5.3.1.4. Outpatient visit days (Screening, Days 8, 15, 22, 29, 36, 43, 50 and V11 of Follow up visit)

- The caloric intake/menu assigned to each participant will be based on the Harris Benedict formula (sedentary lifestyle; to be provided to the site prior to study start) using the participant's body weight measured at screening.
- Participants will not be required to consume all provided food during standard meals.
- When a meal or snack is scheduled at the same time as an ECG, the meal will be provided after the ECGs are completed.
- A standard breakfast will be provided with dosing at approximately the same time each day.
- Lunch will be provided approximately 4 hours after AM dosing (approximately 1200 hours) except on V11 of follow up visit.

5.3.1.5. On Non-visit days and Unscheduled visit

- The study intervention must be administered BID with the morning and evening food, approximately 10-12 hours apart.

5.3.2. Caffeine, Alcohol, and Tobacco

- Caffeine containing products may not be consumed within 2 hours prior to measuring vital signs and ECGs, and may not be consumed on days with MMTT.
- Participants will abstain from alcohol for 24 hours prior to each visit to the site and continue abstaining from alcohol until completion for all procedures of each visit. Except above period, intake of alcohol is permitted in moderation (refer to exclusion criterion 21)

for acceptable amount of alcohol consumption). Participants may undergo an alcohol breath test or blood alcohol test at the discretion of the investigator.

- Participants may use tobacco- or nicotine-containing products, as permitted by the site practices except as noted below.
- Use of these products will not be permitted during frequent sampling procedures (eg, will not be permitted until after the MMTT procedures), and will not be permitted within 2 hours prior to any vital sign and ECG assessments. Use of these products will also not be permitted 2 hours before and 2 hours following any dose of PF-06882961/placebo.

5.3.3. Activity

- Participants will abstain from strenuous exercise (eg, heavy lifting, weight training, calisthenics, aerobics) for at least 48 hours prior to each blood collection for clinical laboratory tests. Walking at a normal pace will be permitted.

5.3.4. Contraception

The investigator or his or her designee, in consultation with the participant, will confirm that the participant has selected an appropriate method of contraception for the individual participant from the permitted list of contraception methods (see [Appendix 4 Section 10.4.4](#)) and will confirm that the participant has been instructed in its consistent and correct use. At time points indicated in the [SOA](#), the investigator or designee will inform the participant of the need to use highly effective contraception consistently and correctly and document the conversation and the participant's affirmation in the participant's chart (participants need to affirm their consistent and correct use of at least 1 of the selected methods of contraception). In addition, the investigator or designee will instruct the participant to call immediately if the selected contraception method is discontinued or if pregnancy is known or suspected in the participant or partner.

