1.3. Schedule of Activities

The SOA tables ([Table 1](#) and [Table 2](#)) provide an overview of the protocol visits and procedures. Refer to the **STUDY ASSESSMENTS AND PROCEDURES** section of the protocol for detailed information on each procedure and assessment required for compliance with the protocol.

The investigator may schedule visits (unplanned visits) in addition to those listed in the SOA table, in order to conduct evaluations or assessments required to protect the well-being of the participant.

Table 1. Overall Schedule of Activities

Protocol Activity (See Appendix 10 for abbreviations)	Screen	Study Day (all activities at 0H [prior to AM meals/dosing] unless otherwise specified)										Follow Up		ET	
Visit	V1	V2		V3	V4	V5	V6	V7	V8	V9	V10		V11	V12 ^a	
Weeks Relative to Dosing on Day 1		0		1	2	3	4	5	6	7	8		9-10	12-13	
Days Relative to Dosing on Day 1 ^b	-28 to -3	Day -2 to Day 1	2	8	15	22	29	36	43	50	Day 55 to Day 56	57	58	63 - 70	84 - 91
Informed consent & demography	x														
Review of eligibility criteria	x														
Discharge from inpatient stay		x										x			
Outpatient visit (after ≥8-H fast)	x		x	x	x	x	x	x	x	x		x			
Adverse event monitoring	x		x	x	x	x	x	x	x	x		x	x	x	x
Medical history	x														
Review prior and concomitant treatments	x		x	x	x	x	x	x	x	x		x	x	x	x
Review drug, alcohol, tobacco use	x		x	x	x	x	x	x	x	x		x	x	x	x
Review contraception use (females only)	x		x	x	x	x	x	x	x	x		x	x	x	x
Review dosing diary, glucometer & glucose log			x	x	x	x	x	x	x	x		x ^c		x	
Glucose measurement (8 hours fasting, via glucometer, on site)			x	x	x	x	x	x	x	x		x			
Physical examination (height at screening only) ^d	x											x		x	x
CCI															
Supine vital signs ^f	x														
Supine 12-lead ECG ^g	x														
Dispensation of study intervention															
On-site study intervention administration with meal ^h															
Standardized meals/snacks												x	x		
Blood sampling for:															
CCI															
Hematology, chemistry (inc. eGFR)	x														
CCI															
Lipids, TSH, free T4, calcitonin, amylase, lipase, TBA, PT/INR/aPTT	x														

PFIZER CONFIDENTIAL

Protocol Activity (See Appendix 10 for abbreviations)	Screen	Study Day (all activities at 0H [prior to AM meals/dosing] unless otherwise specified)										Follow Up		ET	
		V2		V3	V4	V5	V6	V7	V8	V9	V10		V11	V12 ^a	
Visit		V1	0	1	2	3	4	5	6	7	8	9-10	12-13		
Weeks Relative to Dosing on Day 1															

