10.4.2. Female Participant Reproductive Inclusion Criteria

A female participant is eligible to participate if she is not pregnant or breastfeeding, and at least 1 of the following conditions applies:

- Is not a WOCBP (see definitions below in Section 10.4.3).

OR

- Is a WOCBP and using a contraceptive method that is highly effective (with a failure rate of $<1\%$ per year), preferably with low user dependency, as described below during the intervention period and for at least 28 days after the last dose of study intervention, which corresponds to the time needed to eliminate any reproductive safety risk of the study intervention(s). The investigator should evaluate the effectiveness of the contraceptive method in relationship to the first dose of study intervention.
- Is a WOCBP and using a contraceptive method that is highly effective (with a failure rate of $<1\%$ per year), with high user dependency, as described below during the intervention period and for at least 28 days after the last dose of study intervention, which corresponds to the time needed to eliminate any reproductive safety risk of the study intervention(s). In addition, a second effective method of contraception, as described below, must be used. The investigator should evaluate the effectiveness of the contraceptive method in relationship to the first dose of study intervention.

The investigator is responsible for review of medical history, menstrual history, and recent sexual activity to decrease the risk for inclusion of a woman with an early undetected pregnancy.

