10.4.4. Contraception Methods

Contraceptive use by men or women should be consistent with local availability/regulations regarding the use of contraceptive methods for those participating in clinical trials.

Highly Effective Methods That Have Low User Dependency

1. Implantable progestogen-only hormone contraception associated with inhibition of ovulation*.
2. Intrauterine device.
3. Intrauterine hormone-releasing system.
4. Bilateral tubal occlusion.

5. Vasectomized partner.

- Vasectomized partner is a highly effective contraceptive method provided that the partner is the sole sexual partner of the WOCBP and the absence of sperm has been confirmed. If not, an additional highly effective method of contraception should be used. The spermatogenesis cycle is approximately 90 days.

*) Not approved in Japan.

Highly Effective Methods That Are User Dependent

1. Combined (estrogen- and progestogen-containing) hormonal contraception associated with inhibition of ovulation.
 - Oral;
 - Intravaginal*;
 - Transdermal*;
 - Injectable*.
2. Progestogen-only hormone contraception associated with inhibition of ovulation.
 - Oral*;
 - Injectable*.
3. Sexual abstinence.
 - Sexual abstinence is considered a highly effective method only if defined as refraining from heterosexual intercourse during the entire period of risk associated with the study intervention. The reliability of sexual abstinence needs to be evaluated in relation to the duration of the study and the preferred and usual lifestyle of the participant.

*) Not approved in Japan.

[figure not shown]
One of the following effective barrier methods must be used in addition to the highly effective methods listed above that are user dependent:

- Male or female condom with or without spermicide;
- Cervical cap*, diaphragm*, or sponge with spermicide*;
- A combination of male condom with either cervical cap*, diaphragm*, or sponge with spermicide* (double-barrier methods).

*) Not approved in Japan.

CCI

■ 

■ 

■ 

■ 

■ 

■ 

■ 

■ 

■ 

■ 

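### The contraception affirmation in Protocol Section 5.3.4 can be met with one method, while Appendix 4 requires two when the highly effective method is user dependent

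*Protocol*

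**What the plan says.** Section 5.3.4 of the protocol governs contraception during the study. At the time points in the Schedule of Activities, the site reminds the participant that highly effective contraception is needed and charts her response. The sentence closes with the criterion for that response: "participants need to affirm their consistent and correct use of at least 1 of the selected methods of contraception". The same paragraph adds that the site "will instruct the participant to call immediately if the selected contraception method is discontinued".

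Section 10.4.2 gives two routes by which a woman of childbearing potential may take part. On the first, her highly effective method has low user dependency, and no second method is mentioned. On the second, her method has high user dependency, and the text goes on: "In addition, a second effective method of contraception, as described below, must be used". Both routes apply "during the intervention period and for at least 28 days after the last dose of study intervention". Section 10.4.4 repeats the point after its list of methods: "One of the following effective barrier methods must be used in addition to the highly effective methods listed above that are user dependent".

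Section 4.2.1 explains why this matters to the sponsor. It notes that marketed drugs of the class are contraindicated in pregnancy, says that "measures will be taken to limit the risk of pregnancy in the female population enrolled", and points to the Schedule of Activities and Appendix 4 as the place where those measures are found.

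**The concern.** The recurring affirmation is how the Appendix 4 requirement is followed up after entry. Section 5.3.4 sets one threshold for everyone and does not separate the two routes. Because it speaks of the selected methods in the plural, it plainly covers a woman who selected two, and it accepts either one of them.

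A site that follows 5.3.4 to the letter could therefore record a satisfactory affirmation from a woman who no longer meets 10.4.2. The reminder in the same sentence is about highly effective contraception, and barrier methods are not on either highly effective list in 10.4.4. A woman who has stopped the barrier but kept the other method would thus not be prompted about what she has stopped. At stake is whether a pregnancy-prevention measure that the protocol relies on works as Appendix 4 describes, during dosing and in the weeks after it.

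**Working it through.** There is no figure in the plan to reproduce. The check sets the passages side by side and then looks for any other provision that would close the gap.

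**Step 1. Methods required against methods affirmed.**

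| Route in 10.4.2 | Required by Appendix 4 | Enough for the 5.3.4 affirmation | Shortfall |
|---|---|---|---|
| Low user dependency | 1 | 1 | 1 − 1 = 0 |
| High user dependency | 2 | 1 | 2 − 1 = 1 |

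The texts agree on the first route and differ by one method on the second.

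**Step 2. Who is on the second route.** The study runs at a single site in Japan. Among the user-dependent methods in 10.4.4, only combined oral contraception and sexual abstinence are not marked as unapproved in Japan. Both fall under the two-method text. For a woman who is abstinent as 10.4.4 defines it, failing to affirm a barrier has little practical meaning, so the working case is a woman on combined oral contraception plus a barrier.

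**Step 3. Whether another provision would show a dropped method.**

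- *Schedule of Activities, Tables 1 and 2.* A review of contraception use is listed from screening through follow-up and early termination, and at the two inpatient admissions. It is not confined to one method, so a site may well ask about both. The tables give no criterion for a satisfactory answer; the only one stated is in 5.3.4.
- *Self-report, Section 5.3.4.* The instruction to call refers to the selected method in the singular and depends on the participant.
- *Concomitant treatment, Section 6.5.* Stop dates are recorded and participants are asked at each clinic visit. This could show that an oral contraceptive was stopped. It would not show that a barrier was.
- *Pregnancy tests, Tables 1 and 2 and Section 8.2.7.* A negative result is needed at Visits 2 to 10 to continue. The test detects pregnancy, not the loss of a method.
- *Section 7.1.* Intent to become pregnant and confirmed pregnancy are listed as reasons to stop study intervention. Loss of a required method is not mentioned.

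**Step 4. Result.** A stopped oral contraceptive has a fair chance of being noticed through the medication record or the call. A stopped barrier would come to light only through the participant's own report or a site that asks beyond what 5.3.4 requires.

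**The case against.** The strongest reply is that the passages can all be obeyed at once. On this view, the one-method wording is a floor for documentation, written to fit the low-user-dependency route. The Appendix 4 duty continues by its own terms, inclusion criterion 1 and Section 5.3.4 both refer the site to Appendix 4, and nothing in 5.3.4 waives the second method. All of that is correct. It shows that the requirement on the participant survives. It does not show that the recorded affirmation tests it, because 5.3.4 applies the same floor to women on both routes.

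A second reply is that other safeguards exist. That also stands in part. A reader might infer from the mismatch that a woman who drops a method passes every check and goes on dosing. The documents do not support that: the open review, the instruction to call, the medication record and the pregnancy-test requirement can each interrupt that course. What remains is that none of them is a dependable check on the barrier.

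A reader might also infer that every hormonal user needs two methods. That is not so, since 10.4.4 lists the intrauterine hormone-releasing system as a low-user-dependency method without the mark for lack of approval in Japan. Nor does Section 4.2.1 make the pregnancy-prevention measures a condition of enrolling women of childbearing potential. It bases their enrolment on the available embryo-fetal toxicity studies and then adds the measures as a precaution.

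**Conclusion.** The inconsistency is real and narrow. For women of childbearing potential on a user-dependent method, the affirmation in 5.3.4 can be satisfied with one method fewer than 10.4.2 and 10.4.4 require. For women on a low-user-dependency method there is no conflict.

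The conclusion rests on a literal reading of 5.3.4, and on the absence of any stricter criterion elsewhere in the protocol. A site manual or visit checklist, which this review has not seen, might already ask about each method.

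The size of the risk cannot be computed. The documents give no expected number of women of childbearing potential, no mix of methods and no failure rate for one method used alone. It is tempting to say that one resulting pregnancy would cost an arm 1 of about 9 participants (1/9 = 11%). That is the weight of any single discontinuation in an arm of this size, not a measure of this gap, and a dropped method is not itself a listed reason to stop. No endpoint, analysis or sample-size statement is affected. The point deserves correction because it weakens a stated safety measure and is cheap to put right.

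**What to change.** Reconcile Section 5.3.4 with Sections 10.4.2 and 10.4.4, so that the affirmation documented at each contraception review and the requirement for that participant's category agree. How the passages are brought into line is for the sponsor's clinical team; this review takes no position on which contraceptive rule is right.

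The cost is about one sentence in the protocol and a matching line in the visit checklist. No visit, sample or test is added, and the SAP does not change.
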